6.4.2.3. Time to Deterioration in FHSI-8

Time to deterioration in FHSI-8 total score is defined as the time from the date of randomization to the first date observing a decrease of ≥ 3 points from baseline. In case of no FHSI-8 deterioration, the subject will be censored at the time of the last FHSI recording. Additionally, the deterioration threshold and clinically meaningful difference will be evaluated in the trial population as described in the Psychometric Statistical Analysis Plan.

The deterioration criteria that FHSI-8 total score decrease of ≥ 2 or 4 points will be used as sensitivity analyses.

Other patient-focused outcome analysis is defined in Section 6.4.2.7.

6.4.2.4. Time to Deterioration in ECOG PS

Time to deterioration in ECOG PS is defined as the time from the date of randomization to the first date observing ECOG PS ≥ 2 (that is, deterioration from baseline status of 0 or 1). In case of no PS greater than 2, the subject will be censored at the time of the last PS recording.

The deterioration criteria that the PS change from baseline ≥ 2 or PS change to ≥ 3 will be used as sensitivity analysis.

6.4.2.5. Objective Response Rate and Disease Control Rate

The ORR will be calculated as the number of patients who achieve a best response of complete response (CR) or partial response (PR) using investigator response assessments divided by the total number of patients randomized to that study arm. Disease control rate (DCR) will be calculated as the number of patients who achieve a best response of CR, PR, or SD using

investigator response assessments divided by the total number of patients randomized to that study arm. The Response Evaluation Criteria In Solid Tumors Version 1.1 (RECIST 1.1) guideline will be followed in this clinical trial. Patients who do not have a tumor response assessment for any reason are considered non-responders and are included in the denominator when calculating the ORR or DCR.

A PR or CR will not require confirmation to be considered to be a response. In the case of SD, follow-up measurements must have met the SD criteria at least once after study entry at a minimum interval of 6 weeks (that is, 6 weeks – 3 days = 39 days as allowed per protocol) from randomization to assign a best response of SD. If there are no postbaseline scans available for a patient, then the best response will be not evaluable (NE).

6.4.2.6. Time to Radiographic Progression

Time to radiographic progression (TTP) is defined as the time from the date of randomization until the date of radiographic progression according to RECIST 1.1. Censoring rules are described in [Table 5](#).

Table 5. Rules for Determining Date of Progression or Censor for TTP

Situation	Event / Censor	Date of Event or Censor
Tumor progression	Event	Earliest date of PD
No tumor progression (regardless of death)	Censored	Date of last adequate radiological assessment or date of randomization (whichever is later)
unless		
No baseline radiological tumor assessment available	Censored	Date of randomization
No adequate post baseline radiological tumor assessment available	Censored	Date of randomization
New anticancer treatment started and no tumor progression within 14 days	Censored	Date of adequate radiological assessment prior to (start of new therapy +14 days) or date of randomization (whichever is later)
Tumor progression documented immediately after 2 or more scan intervals following last adequate radiological tumor assessment or randomization (whichever is later)	Censored	Date of last adequate radiological assessment or date of randomization (whichever is later)

Abbreviations: CR = complete response; PD = progressive disease; PFS = progression-free survival; PR = partial response; SD = stable disease.

Notes:

1. Clinical progression (that is, symptomatic progressions, which are not radiologically confirmed) will not be considered as progressions.
2. Adequate radiological tumor assessment refers to an assessment with one of the following responses: CR, PR, SD, or PD.
3. If target, non-target and new lesion assessments have different dates within a visit, then the earliest of those dates will be considered as the date of the tumor assessment if the assessment for that visit is PD; otherwise the latest date will be used.

6.4.2.7. Patient-Focused Outcomes (PFOs)

Patient-reported symptoms will be assessed using the Functional Assessment of Cancer Therapy (FACT) Hepatobiliary Symptom Index-8 (FHSI-8). The FHSI-8 is a 5-point, 0-4 assessment (a higher score representing high symptom burden) for 8 symptoms including some more specific to hepatobiliary cancer (jaundice, stomach pain/discomfort) and some that are associated with generalized advanced/metastatic malignancy (weight loss, fatigue) (Yount et al. 2002).

The FHSI-8 is scored to obtain a single FHSI-8 total score of 0 to 32, with a higher score representing low symptom burden. The FHSI-8 will be scored according to the developer's guidelines, including imputation by prorating if >50% of items (5 items or more out of the 8) are completed.

The prespecified minimal clinically important difference from baseline in FHSI-8 total score is approximately 10% of the range of the scale, or 3 points (Steel et al. 2005).

Scores for each postbaseline time point will be compared to the baseline value and categorized as follows:

Deterioration: Defined as a decrease of 3 points or more

Improvement: Defined as an increase of 3 points or more

Stable: Defined as no change or increase/decrease <3 points

The best response across all time points will be obtained by categorizing the best total score as deterioration, improvement, or stable. The worst response will be similarly obtained by categorizing the worst total score.

Additional meaningful change thresholds will also be derived from the trial population as described in the Psychometric Statistical Analysis Plan. The time to deterioration analysis will be performed using thresholds derived from these analyses in addition to the prespecified 3-point decrease.

Time to deterioration for individual item of FSHI-8 is the time from the date of randomization to the first date observing deterioration of each item, with the deterioration threshold defined as a decrease in one categorical response from baseline of each item. In case of no deterioration, the subject will be censored at the time of the last assessable FSHI-8 individual item recording.

EuroQol – 5 Dimensions 5 Level (EQ-5D-5L)

Additionally, patients' health status will be assessed using EQ-5D-5L. EuroQol – 5 Dimensions index score is calculated from a set of item weights to derive a scale of 0 to 1, with 0 representing death and 1 representing perfect health, with the possibility of negative scores. The index score will be based on the value set for England, where the lowest possible value is -0.281 (Devlin et al. 2017). The visual analog scale (VAS) is scored from 0 (*worst imaginable health state*) through 100 (*best imaginable health state*) to represent the patient health condition.

For FSHI-8 and EQ-5D-5L, other than baseline visit and end of treatment visit, a visit window is applied. If the actual assessment date falls in the window of study days $[(X-1)*7-20, (X-1)*7 + 21]$, where $X = 7, 13, 19, \dots$, the visit will be presented as Week X. If there are multiple assessments within 1 visit window, the last assessment will be used in the summary by visit.

For percentage compliance of the FSHI-8 and EQ-5D-5L, instruments with at least 1 item completed will be considered as having been completed. No other adjustment or imputation for missing data will be performed. To evaluate the impact of missing data on results, sensitivity analyses will be performed from the following imputations: last observation carried forward, worst observation carried forward, and multiple imputation using Markov Chain Monte Carlo methodology.

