10.2.1. Functional Assessment of Cancer Therapy (FACT) Hepatobiliary Symptom Index-8 (FHSI-8)

The FHSI-8, a self-administered questionnaire with specific focus regarding the most frequent and concerning symptoms experienced by patients with hepatobiliary malignancies, involves a 5-point assessment for 8 symptoms, including symptoms more specific to hepatobiliary cancer (jaundice, stomach pain/discomfort) and symptoms associated with generalized advanced/metastatic malignancy (weight loss, fatigue; Yount et al. 2002). The 8 items on the FHSI-8 were drawn from the larger FACT-G and 18-item hepatobiliary subscale (Cella et al. 1993; Heffernan et al. 2002). These items were selected based on relative clinical importance ratings provided by a multinational group of 95 hepatobiliary cancer specialists. Results from the 8-item FHSI-8 correlated significantly with the larger FACT-G and hepatobiliary subscale instruments and demonstrated internal consistency, reliability, and convergent validity. Additionally, the FHSI-8 was utilized in the multinational REACH study to demonstrate a delay in time to symptomatic deterioration in patients with elevated baseline AFP treated with ramucirumab versus placebo. The FHSI-8 was also included in the multinational SHARP study comparing sorafenib versus placebo in patients with advanced, unresectable HCC (Llovet et al. 2008b).

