Appendix 2.	Clinical Trial Registry Analyses	40

Redacted Version

3. Revision History

Statistical analysis plan (SAP) Version 1 was approved prior to first meeting of the independent data monitoring committee (IDMC).

Version 2 was approved prior to the database lock to assess primary objective to update the following components:

- Added time to deterioration in Functional Assessment of Cancer Therapy (FACT) Hepatobiliary Symptom Index-8 (FHSI-8) total score and Eastern Cooperative Oncology Group performance status (ECOG PS) as secondary projectives
- Updated Region 1 area
- Revised determination of sample size
- Revised Per-protocol population definition and criteria
- Revised the method to summarize dose delay and dose omission
- Removed the last progression-free survival (PFS) sensitivity analysis
- Revised the definition of time to deterioration
- Clarified the criteria of stable disease (SD) as the best overall response
- Revised patient-focused outcomes analysis definition
- Revised missing data handling
- Revised the testing sequence of secondary endpoints
- Added time to deterioration of FHSI-8 individual item analysis
- Revised the study exposure analysis
- Revised overall summary of adverse events
- Revised summary of death, serious adverse events (SAEs), and adverse events of special interest (AESI)
- Added the analysis of treatment-emergent anti-drug antibodies
- Added reference

4. Abbreviations

Term	Definition
AE	adverse event
AESI	adverse event of special interest
AFP	alpha-fetoprotein
BCLC	Barcelona Clinic Liver Cancer (staging)
BOR	best overall response
BSC	best supportive care
CI	confidence interval
CP	Child-Pugh
CR	complete response
CRF/eCRF	case report form (electronic)
DCR	disease control rate
ECG	electrocardiogram
ECOG PS	Eastern Cooperative Oncology Group Performance Status
EQ-5D-5L	EuroQol 5-Dimension 5-Level
FACT	Functional Assessment of Cancer Therapy
FHSI-8	FACT Hepatobiliary Symptom Index-8
HCC	hepatocellular carcinoma
HR	hazard ratio
IC	inclusion criterion
ICF	inform consent form
IDMC	Independent Data Monitoring Committee
ITT	intent-to-treat
IWRS	Interactive Web Response System
KM	Kaplan-Meier
LVEF	left ventricular ejection fraction

MedDRA®	Medical Dictionary for Regulatory Activities
MUGA	Multiple Gated Acquisition Scan
NE	not evaluable
NCI-CTCAE	National Cancer Institute Common Terminology Criteria for Adverse Events
ORR	objective response rate
OS	overall survival
PD	progressive disease
PFS	progression-free survival

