6.5.5.1. FHSI-8 Analyses

The proportion of patients in each arm with deterioration in scores, improvement in scores, and stable scores at specific time points will be presented both in a summary table and graphically using stacked bar charts. The proportion of patients who deteriorated at each assessment time point may be compared using Fisher's exact test. Patients with no data will be considered deteriorated.

FHSI-8 score will be summarized descriptively at each assessment time by treatment arm, as well as changes from pre-treatment visit, provided at least 30% of the patients have an FHSI-8 score at that time point. Best and worst responses across all the visits will also be summarized in a table.

The time to deterioration of FHSI-8 individual item will be compared between the treatment groups from stratified and unstratified log-rank tests. The HR and 95% CIs will be estimated using Cox's PH model, covariates may include assigned treatment and baseline score.

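### As written, the SAP's FHSI-8 item rule times a fall on a scale where higher is worse, so it counts improvement as deterioration unless items are reversed first, which the SAP does not state

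*SAP*

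**What the plan says.** SAP 6.4.2.7 gives two scales that run in opposite directions. The items are a "0-4 assessment (a higher score representing high symptom burden) for 8 symptoms". They are combined into an "FHSI-8 total score of 0 to 32, with a higher score representing low symptom burden". For the total, a fall of 3 points or more is deterioration, which fits the total's direction.

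The same section then defines time to deterioration for each single item, "with the deterioration threshold defined as a decrease in one categorical response from baseline of each item". SAP 6.5.5.1 puts that definition to use: "The time to deterioration of FHSI-8 individual item will be compared between the treatment groups from stratified and unstratified log-rank tests". It adds a Cox model for the hazard ratio.

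On scoring, SAP 6.4.2.7 says: "The FHSI-8 will be scored according to the developer's guidelines". This sentence comes directly after the description of the total and continues with the rule for prorating incomplete forms. It does not mention the item analyses.

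The item analysis is new in SAP version 2; the revision history (SAP 3) lists "Added time to deterioration of FHSI-8 individual item analysis". Protocol 10.2.1 says only that the questionnaire "involves a 5-point assessment for 8 symptoms" and gives no direction. Protocol 12.2.10.1 defines deterioration on the 3-point rule and plans no item analysis.

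**The concern.** The clause in SAP 6.4.2.7 is the only specification of the item endpoint in either document. It carries over the direction of the total (lower is worse) to a scale that the same section describes as running the other way. A programmer who applies it to the 0 to 4 response would time the first relief of each symptom and label it deterioration.

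Each of the eight item hazard ratios would then be read in the wrong direction. The item results are meant to show which symptoms lie behind the total score, and they could appear to contradict it.

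**Working it through.** **Inputs, all from SAP 6.4.2.7.** There are 8 items scored 0 to 4, higher worse. The total runs 0 to 32, higher better. Total deterioration is a fall of at least 3. Item deterioration is a fall of one category, read here as at least one.

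**Step 1. Reproduce the plan's own figures.** 8 × 0 = 0 and 8 × 4 = 32, the stated range. 10% × 32 = 3.2, which matches the stated threshold of about 10% of the range, or 3 points.

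**Step 2. Link items and total.** Raw items are higher-worse and the total is higher-better over the same range, so the total must be the sum of (4 − item). Reversal is therefore implied for the total.

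**Step 3. Enumerate one item.** There are 5 × 5 = 25 baseline-to-follow-up pairs.
- Worsenings (follow-up above baseline): 4 + 3 + 2 + 1 + 0 = 10.
- Improvements (follow-up below baseline): 0 + 1 + 2 + 3 + 4 = 10.
- Unchanged: 5.

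| Rule | Worsenings flagged | Improvements flagged |
|---|---|---|
| Fall of ≥1 on the 0–4 item as described | 0 of 10 | 10 of 10 |
| Rise of ≥1 on the 0–4 item | 10 of 10 | 0 of 10 |
| Fall of ≥1 on the reversed item (4 − item) | 10 of 10 | 0 of 10 |

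The last two rows flag the same pairs. Under the first row, a patient with the lowest burden at baseline (item = 0) could never have an event, although that patient has the most room to worsen.

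**Step 4. Check against the total.** Start with every item at 2, so the total is 8 × (4 − 2) = 16.

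| Change | Total | Items flagged, raw fall | Items flagged, reversed fall |
|---|---|---|---|
| 3 items worsen by 1 | 13 (−3, deterioration) | 0 | 3 |
| 3 items improve by 1 | 19 (+3, improvement) | 3 | 0 |
| 8 items worsen by 1 | 8 (−8, deterioration) | 0 | 8 |

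On raw items the item rule disagrees with the total in each case. On reversed items it agrees.

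**Step 5. Scope.** The confirmatory sequence in SAP 6.5.3.3 is OS, PFS, time to deterioration in the FHSI-8 total, and time to deterioration in ECOG PS. Item analyses are not in it.

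**Step 6. Two adjacent points in the FHSI-8 text.**
- *Denominator.* For the by-visit proportions SAP 6.5.5.1 states: "Patients with no data will be considered deteriorated". SAP 6.3.1 assigns quality of life to the ITT population. SAP 6.5.5 uses the patients expected at each time point for compliance. SAP 6.5.5.1 does not say which of these is the denominator for the proportions.
- *Change from baseline.* The protocol (Synopsis, Health Outcomes; and 12.2.10.1) plans a between-arm comparison of FHSI-8 change for statistical significance. The SAP compares arms on categories of change: time to deterioration of the total (6.5.3.3.2) and an optional Fisher test by visit (6.5.5.1). Change as a score is only summarized. SAP Section 8 reports no departures from the protocol.

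**The case against.** The strongest reply is that reversal is already built into the SAP. A total on which higher is better can only come from reversed items, scoring follows the developer's guidelines, and the optional baseline-score covariate in SAP 6.5.5.1 suits scored items. On scored items a fall is the correct direction. This stands as evidence of what the authors may have meant. It does not repair the text. The scoring sentence concerns the total, neither 6.4.2.7 nor 6.5.5.1 says that reversed items feed the item analyses, and a categorical response reads most naturally as the answer on the 0 to 4 scale. The guidelines themselves cannot be consulted from these documents.

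It is also fair to say that the enumeration restates the definition and gives no patient-level effect. It shows that the inversion is complete on the literal reading, and no more.

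Four stronger readings are tempting, and the documents do not support them.
- *The item analyses were run the wrong way round.* The documents do not show the programming, and reversal may have been applied.
- *The confirmatory FHSI-8 result is compromised.* That endpoint uses the total, whose direction and rule agree.
- *The no-data rule contradicts the SAP's missing-data policy.* SAP 6.4.3 allows specified exceptions to its observed-data default. The sentence in 6.4.2.7 ruling out other imputation follows a sentence on compliance and can be read as limited to it. SAP 6.4.2.7 also plans several imputation-based sensitivity analyses. Counting missing patients as deteriorated is a recognised composite choice. Only the missing denominator is a clear gap.
- *A protocol test was dropped without being declared.* The protocol names no specific test, leaves detail to the SAP, and the SAP does compare baseline-referenced change by category. Since Protocol 12.2.10.1 lists time to deterioration separately, it is fair to ask which analysis meets the planned comparison, but an omission is not proven.

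**Conclusion.** The item rule is wrong as written and should be corrected. On the only item direction that either document states, it flags 0 of 10 possible worsenings and 10 of 10 possible improvements, for each of the eight items. These are counts of score pairs, not patients; how far any hazard ratio would move cannot be derived from the documents. The count assumes that the threshold means at least one category. If it meant exactly one, the rule would flag 4 improvements (1 to 0, 2 to 1, 3 to 2, 4 to 3) and still no worsening.

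The conclusion depends on items being analysed on the scale described. If they are reversed first, the rule is right and the defect is one unstated step. Only supportive, non-gated analyses are affected. The denominator and the comparison of change are minor points to reconcile.

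**What to change.** In SAP 6.4.2.7, define item deterioration as an increase of at least one category from baseline on the raw 0 to 4 item (equivalently, a decrease of at least one category on the reverse-scored item, 4 − item). Name the item score used there, and repeat the name in 6.5.5.1, where the baseline score may enter the Cox model.

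In the same revision:
- State in 6.5.5.1 the denominator for the by-visit proportions that count patients without data as deteriorated.
- Either specify the between-arm comparison of FHSI-8 change from baseline that the protocol plans, or state in SAP Section 8 which categorical analysis takes its place. The choice is the sponsor's.

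The cost is one clause for the main point, one sentence for the denominator, and one sentence or one analysis for the comparison. No new data and no protocol amendment are needed.

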6.2.2. Determination of Sample Size

The primary objective of this study is to compare ramucirumab versus placebo in terms of OS in patients with advanced HCC after intolerance or progression on prior sorafenib. The sample size was determined based on the following assumptions:

- hazard ratio (treatment/control) of 0.67, with median OS of 4.5 months in the placebo arm and 6.7 months in the ramucirumab arm
- the randomization ratio is 2:1 (ramucirumab:placebo)
- the overall significance level will be controlled at 1-sided 0.025 (2-sided 0.05)
- the Type II error rate is 20%; that is, the statistical power of the trial is set to 80%

Under the assumptions above, the final analysis will be performed when at least 221 deaths have been observed. Therefore, the study will randomize approximately 279 patients (that is, 20% censoring rate including dropouts, with approximately 186 patients randomized to the ramucirumab arm and 93 patients randomized to the placebo arm).

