6.5.3.3. Secondary Efficacy Endpoints

A gatekeeping approach to selected secondary endpoints will be applied so as to protect the study-wise type I error rate and to enable inferential statements; each hypothesis is inferentially tested only if each of the preceding hypotheses were rejected. The sequential order of the confirmatory testing after OS in the ITT population will be: 1) PFS in the ITT population; 2) time to deterioration in FHSI-8 total score in the ITT population; and 3) time to deterioration in ECOG PS in the ITT population. Secondary endpoints will be analyzed at the same time as OS and at the same level of significance (1-sided 0.025).

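### For time to deterioration in FHSI-8, carrying total scores forward cannot add an event, and no listed missing-data analysis tests informative dropout or is told to stop at death

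*SAP*

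**What the plan says.** The missing-data paragraph closes SAP 6.4.2.7. Its stated purpose is "To evaluate the impact of missing data on results", and its content is that "sensitivity analyses will be performed from the following imputations: last observation carried forward, worst observation carried forward, and multiple imputation" by Markov chain Monte Carlo. It covers FHSI-8 and EQ-5D-5L together. It does not say which endpoints are meant, whether items or totals are imputed, how far forward imputation runs, or what happens at death.

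Time to deterioration in FHSI-8 total score is a confirmatory endpoint. SAP 6.5.3.3 places it directly after PFS in the testing order: "2) time to deterioration in FHSI-8 total score in the ITT population". The threshold is given in 6.4.2.7 as "Deterioration: Defined as a decrease of 3 points or more". The censoring rule in 6.4.2.3 is "In case of no FHSI-8 deterioration, the subject will be censored at the time of the last FHSI recording"; it makes no separate provision for death.

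The other sensitivity analyses named for this endpoint change the threshold to 2 or 4 points or use thresholds from the psychometric plan (6.4.2.3 and 6.4.2.7), drop the stratification, or may add covariates (6.5.3.3.2). Under Protocol Attachment 1, questionnaires are completed at baseline, every 6 weeks on treatment and once at the start of short-term follow-up. None is scheduled later.

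**The concern.** Reporting stops when treatment stops, and treatment usually stops because of progression, toxicity, declining performance status or death. Censoring at the last questionnaire is therefore likely to be related to how the patient is about to feel. A missing-data sensitivity analysis should ask whether the treatment comparison survives if patients who stopped reporting went on to deteriorate.

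Two of the three listed methods cannot represent that case when applied to total scores. The third assumes that, given the observed data, patients who stopped reporting would have behaved like those who continued. If the gate reaches FHSI-8 and the log-rank test is significant, the report would have no analysis showing how much unobserved deterioration the result can absorb.

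The missing death rule is a second problem. Without one, a programmer could fill in symptom or utility scores at visits after death, in different proportions by arm.

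**Working it through.** **1. Can carry-forward of totals add an event?** Let B be the baseline total and Y1, …, Yk the observed post-baseline totals. A patient without an event has every Yj > B − 3. The last observed score Yk and the worst, min(B, Y1, …, Yk), both exceed B − 3, so no filled-in visit can be an event. A gap before a later real event is filled with a non-deteriorated score, so no event moves earlier. A patient with only a baseline score gets a change of 0. The same argument holds for thresholds of 2 or 4 points. Events added: 0.

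A simulation agreed (8 visits, intermittent gaps plus dropout, three assumed scenarios of 200,000 patients each):

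| Method | New events per 200,000 |
|---|---|
| LOCF, total score | 0, 0, 0 |
| WOCF, total score | 0, 0, 0 |
| WOCF, item by item | 6,218 to 21,987 |
| Simple MAR imputation, one draw | 20,532 to 112,387 |

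Only the two zeros are independent of the assumed parameters. Item-level WOCF can add events because the worst items from different visits may be combined.

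**2. What does the extra event-free time do to the hazard ratio?** Assume exponential deterioration (rate λ) and, independently, exponential stopping of reporting (rate σ), with rate = ln 2 / median. The share with an observed event by time H is

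P = λ/(λ+σ) × [1 − e^(−(λ+σ)H)].

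After carry-forward to H nobody is censored earlier, so the apparent cumulative hazard is −ln(1 − P). Assumed inputs: H = 12 months; median time to deterioration 4.5 months on placebo (λ = 0.1540) and 6.0 on ramucirumab (λ = 0.1155), a true hazard ratio of 0.75.

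| Median time to stopping, placebo / ramucirumab (months) | P placebo | P ramucirumab | Ratio of cumulative hazards |
|---|---|---|---|
| 2.5 / 4 | 0.355 | 0.388 | 0.490/0.439 = 1.12 |
| 3 / 3 | 0.396 | 0.328 | 0.398/0.504 = 0.79 |
| 4 / 2.5 | 0.461 | 0.291 | 0.345/0.619 = 0.56 |

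Simulating the same three cases with 6-weekly visits, 2:1 allocation and a Cox model gave 0.77 in each case with the planned censoring, and 1.17, 0.80 and 0.55 after carry-forward. Another simulation on similar assumptions, with placebo stopping earlier, moved from 0.78 to 1.20. In my three cases stopping is independent of deterioration, so the planned analysis was sound and carry-forward did the damage.

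**3. How many patients does a death rule concern?** The SAP 6.2.2 assumptions are coherent. Schoenfeld's formula gives (1.960 + 0.842)² / [(2/3)(1/3)(ln 0.67)²] = 7.849/0.03564 = 220.2, so 221 deaths as stated, and 4.5/6.7 = 0.672. The plan is "with median OS of 4.5 months in the placebo arm and 6.7 months in the ramucirumab arm". With exponential survival, P(dead by t) = 1 − 2^(−t/median), taking Week X as (X − 1) × 7 days and 30.4375 days per month:

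| Visit | Months | Placebo | Ramucirumab |
|---|---|---|---|
| Week 7 | 1.38 | 19% | 13% |
| Week 13 | 2.76 | 35% | 25% |
| Week 19 | 4.14 | 47% | 35% |
| Week 25 | 5.52 | 57% | 44% (43.5) |

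With the earlier study's AFP-high medians (4.2 and 7.8 months, Protocol Section 5), Week 19 becomes 50% versus 31%. These are shares dead, not shares imputed: some patients will have deteriorated before death.

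**The case against.** The strongest reply is about scope. The imputation sentence follows the visit windows and the compliance rule, and the time-to-deterioration sections list their own sensitivity analyses without referring to it. It may have been meant only for by-visit scores, where carry-forward does change the summaries. That reading is available. But 6.4.2.7 also discusses time-to-deterioration thresholds, and the sentence speaks of results without limit. If the narrow reading is right, the gated endpoint has no missing-data sensitivity analysis at all.

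There are also real safeguards. By-visit deterioration proportions count patients with no data as deteriorated (SAP 6.5.5.1), score summaries need at least 30% of patients with a score, and the main summaries use observed data. Invented scores could enter only sensitivity tables.

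Four stronger readings are tempting and not supported:

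- **That none of the three methods can add an event.** Multiple imputation can, and so can item-level WOCF; the level is not stated.
- **That carry-forward will confirm the FHSI-8 result whatever the truth.** Working step 2 shows that it can reverse a real benefit as easily as exaggerate one.
- **That the SAP directs imputation past death.** It is silent, and the compliance denominator of patients expected on study could be read as a limit, although it defines compliance and not imputation.
- **That the event argument extends to EQ-5D-5L.** That instrument has no deterioration event; only the question of death applies to it.

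**Conclusion.** The point holds in this form. Applied to FHSI-8 totals, LOCF and WOCF add no deterioration events, by construction, so they cannot show missed deterioration. They can move the hazard ratio either way when reporting stops at different times in the two arms. Standard MCMC imputation is useful as a MAR reference but does not test informative dropout, and the threshold, stratification and covariate analyses do not address it either.

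The absence of a death rule matters because, on the design medians and exponential survival, about a third of placebo and a quarter of ramucirumab patients are dead by Week 13. Its reach is limited to sensitivity tables.

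The zero-event result needs no modelling assumption beyond imputation at the level of the total score. The hazard-ratio figures rest on assumed medians, exponential times and a 12-month horizon; they show direction and possible size and do not forecast this trial. That the imputations apply to time to deterioration is the natural reading of the SAP, not an explicit statement.

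**What to change.** For time to deterioration in FHSI-8, replace LOCF and WOCF with delta-adjusted (tipping-point) multiple imputation of scores after reporting stops, only for visits at which the patient was alive. Vary the downward shift, separately by arm, and report the shift at which the conclusion changes. Keep MAR multiple imputation, with the same alive-only limit, as the reference.

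For by-visit FHSI-8 and EQ-5D-5L scores, limit any imputation to patients alive at the visit and report deaths separately.

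The cost is one rewritten SAP paragraph and modest programming, with no new data. The drawback is that the shift range is an assumption: the protocol schedules only one questionnaire after treatment stops, so the trial's own data say little about its plausible size. The range should be fixed before unblinding.
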